10.5 Appendix 6: Pubertal Stages According to Tanner Method

STAGES OF DEVELOPMENT OF SECONDARY SEXUAL CHARACTERISTICS

BOYS: Genital (penis) development

Stage 1. Prepubertal: testes, scrotum, and penis of about same size and proportion as in early childhood.

Stage 2. Enlargement of scrotum and testes. Skin of scrotum reddens and changes in texture.

Stage 3. Enlargement of penis, at first mainly in length. Further growth of testes and scrotum.

Stage 4. Increased size of penis with growth in breadth and development of glans. Testes and scrotum larger; scrotal skin darkened.

Stage 5. Genitalia adult in size and shape.

GIRLS: Breast development

Stage 1. Prepubertal: elevation of papilla only.

Stage 2. Breast bud stage: elevation of breast and papilla as small mound. Enlargement of areola diameter.

Stage 3. Further enlargement and elevation of breast and areola, with no separation of their contours.

Stage 4. Projection of areola and papilla to form a secondary mound above level of breast.

Stage 5. Mature stage: projection of papilla only, related to recession of areola to general contour of breast.

BOTH SEXES: Pubic hair

Stage 1. Prepubertal: vellus over pubes is not further developed than over abdominal wall.

Stage 2. Sparse growth of 1 mg slightly pigmented, downy hair, straight or slightly curled, chiefly at base of penis or along labia.

Stage 3. Considerably darker, coarser, and more curled hair. Hair spreads sparsely over junction of pubes.

Stage 4. Hair now adult in type but area covered is still considerably smaller than in adult. No spread to medial surface of thighs.

Stage 5. Adult in quantity and type with distribution of horizontal (or classically "feminine") pattern.

Stage 6. Spread up linea alba (male-type pattern).

Modified from Tanner JM. Growth at Adolescence. 2nd ed. Oxford: Blackwell Scientific Publications, 1962.

10.6 Appendix 7: Temporary Measures and Procedures Related to COVID-19 Pandemic

This appendix serves as notification of the temporary measures put in place for the conduct of the study during the COVID-19 pandemic and until such time as the situation resolves, at which point the protocol assessments will return to those specified in the current approved protocol effective at that time. The timing of when the pandemic is declared over may vary on a country by country basis as well as between sites in the same country, and as such the temporary measures may remain in place for differing periods of time per country/site. Investigators will determine the feasibility of starting or continuing study treatment on a patient by patient basis, depending on the ability to conduct safety monitoring and providing patients an adequate supply of study treatment, in accordance with local requirements.

Any temporary measure will be reported as a protocol deviation related to COVID-19.

Withdrawal from Study

Participants who are suspected or confirmed to have COVID-19 infection after enrolment will withdraw from the study (see also Section 7.1.2 for temporary withdrawal).

Telemedicine Visit

If the COVID-19 pandemic prevents participants from coming to the site for the Month 9 visit, the investigator will perform a telemedicine visit to collect all important medical information and safety event(s) occurring since the last visit. Besides the Month 9 visit, the participants may delay other visits no more than 2 weeks and preferably within 1 week or be withdrawn from the study as appropriate, as judged by the investigator and agreed with the sponsor.

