7 DISCONTINUATION OF STUDY INTERVENTION AND PARTICIPANT DISCONTINUATION/WITHDRAWAL

7.1 Discontinuation of the Study Intervention

In rare instances, it may be necessary for a participant to permanently discontinue study intervention. If study intervention is permanently discontinued, the participant will remain in the study to be evaluated for efficacy, safety and PK, with assessments described in the SoA. See the SoA for data to be collected at the time of discontinuation of study intervention and follow-up and for any further evaluations that need to be completed.

7.1.1 *Pregnancy*

See Section 8.3.5.

7.1.2 *Temporary Discontinuation*

In case of suspected or confirmed COVID-19 (SARS-CoV-2) infection, the intervention administration may be temporarily discontinued depending on the participant clinical presentation. In some cases, the investigator may request a participant be retested before the intervention administration is resumed.

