9.3 Analysis Sets

For the purposes of analysis, the following analysis sets are defined:

Participant Analysis Set	Description
Screened population	All participants screened (i.e. who signed the ICF)
Safety population	All participants who received at least one dose of study intervention and have at least one postbaseline safety assessment;
ITT/mITT population	The ITT population will include all participants who received at least one dose of study intervention; The modified intention-to-treat (mITT) population will contain all treated participants having a Month 6 post-baseline assessment of the primary efficacy endpoint
PP population	The PP population will contain all participants in the mITT after exclusion of the participants who had major protocol deviations that could potentially affect the primary efficacy endpoint outcome for the participants
PK population	All participants who received at least one dose of study intervention and have at least one valid triptorelin concentration

ICF=informed consent form; ITT=intention-to-treat; mITT=modified ITT; PK=pharmacokinetics; PP=per protocol.

The primary efficacy analysis will be performed on the ITT population. Supportive analysis of the primary efficacy endpoint will be based on the modified intention-to-treat (mITT) and the PP populations.

The secondary efficacy analyses will be based on the ITT population. Supportive analysis of the secondary analyses may be performed on the PP population.

The analyses of safety data will be performed based on the Safety population.

The analyses of PK data will be performed based on the PK population.

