5.7.1.1 Significance Testing and Estimations

For the primary efficacy endpoint, the summary statistics of number and percentage of participants and the exact two-sided 95% confidence interval (CI) for a binomial proportion will be computed by SAS® using the exact binomial distributions on the ITT (primary population of analysis) population.

For secondary efficacy endpoints related to a change at Months 3, 6, 9 and 12 compared to baseline, the descriptive summary statistics (n, mean, SD, median, minimum, maximum) will be calculated on the ITT. Exact two-sided 95% CIs will also be constructed for all secondary endpoints expressed as percentages.

5.7.1.2 *Handling of Dropouts and Missing Data*

Diligent attempts will be made to limit the amount of missing data and to follow-up all treated participants to collect the primary and secondary efficacy endpoints for the statistical analysis.

A Non-responder imputation (NRI) method will be used for all definition of response, for instance, participants who discontinue before evaluation of the endpoint (Month 3, Month 6, Month 9 and Month 12) will be declared non-responder.

5.7.1.3 *Statistical/Analytical Issues*

Adjustments for Covariates

No covariate adjustment analysis is planned in this study.

Interim Analyses and Data Monitoring

No interim analysis will be performed.

Multicentre Studies

No by-centre displays or adjustments for centre are planned for this study.

Multiple Comparisons/Multiplicity

No multiple testing will be performed in this study since this is a single arm study.

5.7.2 *Analysis of Primary Efficacy Endpoint*

5.7.2.1 *Endpoint*

LH suppression: defined as a peak LH ≤ 5 IU/L after intravenous (i.v.) gonadotropin-releasing hormone (GnRH) stimulation in Chinese children with central precocious puberty (CPP).

The primary endpoint is proportion of children with LH suppression at Month 6.

5.7.2.2 *Primary Analysis*

For the primary efficacy endpoint, the summary statistics of number and percentage of participants and the exact two-sided 95% CI for a binomial proportion will be computed by SAS® using the exact binomial distributions on the ITT.

The SAS code to be used could be presented in Appendix A1.

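### Protocol Appendix 7 withdraws a child with suspected or confirmed COVID-19 from the study, while Section 7.1.2 only allows dosing to be paused; a site following the appendix literally turns an infection before Month 6 into a primary-endpoint failure.

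*Protocol*

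**What the plan says.** **Protocol 10.6, Appendix 7, withdrawal paragraph.** Participants "suspected or confirmed to have COVID-19 infection after enrolment will withdraw from the study (see also Section 7.1.2 for temporary withdrawal"). The wording is mandatory, covers a merely suspected infection, and concerns the study rather than the drug.

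**Protocol 7.1.2**, to which that sentence points. For the same trigger, "the intervention administration may be temporarily discontinued depending on the participant clinical presentation", and in some cases "the investigator may request a participant be retested before the intervention administration is resumed". This is optional and concerns dosing only.

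**Protocol 7.1.** "If study intervention is permanently discontinued, the participant will remain in the study to be evaluated for efficacy, safety and PK".

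**Protocol 10.6, elsewhere in the appendix.** The opening paragraph says "Investigators will determine the feasibility of starting or continuing study treatment on a patient by patient basis". The telemedicine paragraph says that, Month 9 apart, "the participants may delay other visits no more than 2 weeks and preferably within 1 week", or be withdrawn as judged appropriate by the investigator and agreed with the sponsor.

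**Scoring.** Protocol 9.3: "The ITT population will include all participants who received at least one dose of study intervention"; the primary analysis is on that population. SAP 5.7.1.2: "participants who discontinue before evaluation of the endpoint (Month 3, Month 6, Month 9 and Month 12) will be declared non-responder". There is no exception for COVID-19. SAP 6.1 sets Month 6 as Day 166 to Day 172, and SAP 6.2 has the last assessment of an early withdrawal entered as visit 90.

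**The concern.** The two COVID-19 rules share a trigger and prescribe different actions. Under Section 7.1.2 an infected child stays in the study and has the Month 6 GnRH test. Under the literal appendix sentence the same child leaves, and the ITT definition and non-responder imputation together record a failure to suppress LH.

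That loss is largely avoidable. Injections are given on Day 1 and at Month 6, and the Month 6 injection follows that visit's other pre-dose assessments. An infection that starts after Day 1 and has resolved by Month 6 therefore need not disturb either dosing or the primary measurement.

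Two sites could each follow the protocol and handle the same child differently, one recording a measured result and the other an imputed failure. The primary test tolerates only six non-responders, so a few such cases matter.

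**Working it through.** **Inputs.** Protocol 9.2 and SAP 2.3: null proportion 0.80, expected proportion 0.93, exact one-sided binomial test at 0.025, 85% power, 5% dropout, 62 treated, 66 enrolled. The number *k* of dosed children withdrawn for COVID-19 before Month 6 is assumed to be 0 to 3.

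**1. The plan's own figure.** Find the smallest *r* with P(X ≥ r | n, 0.80) ≤ 0.025.
- n = 62: r = 56, attained alpha 0.0238, power P(X ≥ 56 | 62, 0.93) = 0.858. The plan's 85% reproduces, and 62/0.95 = 65.3, rounded up to 66.
- n = 66, if all enrolled children are dosed: r = 60, attained alpha 0.0139, power 0.822.

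Either way six non-responders are allowed (62 − 56 = 66 − 60 = 6). At 93% the expected number is already 62 × 0.07 = 4.3 or 66 × 0.07 = 4.6.

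**2. Effect of k imputed failures.** The other n − k children respond at 0.93, and no other Month 6 result is missing. Power is P(X ≥ r | n − k, 0.93); the expected ITT rate is 0.93(n − k)/n.

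| k | Power, 62 treated | ITT rate, 62 | Power, 66 treated | ITT rate, 66 |
|---|---|---|---|---|
| 0 | 86% | 93.0% | 82% | 93.0% |
| 1 | 75% | 91.5% | 70% | 91.6% |
| 2 | 59% | 90.0% | 53% | 90.2% |
| 3 | 40% | 88.5% | 35% | 88.8% |

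**3. Direction.** With k = 1 the attained type I error is P(X ≥ 56 | 61, 0.80) = 0.0105 for 62 treated (from 0.0238) and P(X ≥ 60 | 65, 0.80) = 0.0058 for 66 (from 0.0139). It falls, so the error works against the drug.

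**4. Supportive mITT analysis.** With k = 3 the withdrawn children leave the denominator: 54 of 59 needed, power 77%; or 57 of 63 needed, power 85%. The contrast with 40% or 35% would be visible, but the primary ITT result would not change.

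**5. Could an early-withdrawal test rescue the child?** The EOS/Early Withdrawal column of Protocol Table 2 includes a GnRH test, so stimulated LH may exist. It is entered as visit 90, and no rule in the SAP maps visit 90 to Month 6.

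**6. Other dropout.** The k = 0 row assumes none. If the planned 5% all fell between dosing and Month 6 (an assumption), the success rate would be 0.93 × 0.95 = 0.8835, and power would be 41% (62 treated) or 34% (66 treated) with no COVID-19 withdrawal at all.

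**The case against.** The strongest reply is that the rest of the protocol points to a pause. The appendix sentence cites Section 7.1.2, which has the same trigger and foresees dosing being resumed. The appendix opens by leaving treatment decisions to the investigator case by case. Section 7.2 lists reasons for which a child may be withdrawn and does not name COVID-19. Section 10.3.2 records an infection without a seriousness criterion as non-serious. This stands as evidence of intent. A reader might infer that the plan sets out to score infected children as drug failures; the documents do not support that. What remains is that no sentence cancels the mandatory wording, and the provision it cites is not a withdrawal from the study.

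Second, the power figures are not specific to COVID-19. Any dropout between dosing and Month 6 costs the same under this imputation, as step 6 shows. This also stands. A reader might take the fall from 86% to 40% as the cost of this one sentence. It is not: the counts are assumed, and the starting value ignores other dropout.

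Third, the error is conservative, Appendix 7 is temporary, and the mITT analysis together with the SAP's listings of COVID-19 deviations and missing primary endpoints would expose it. All true. It limits the seriousness but leaves the primary ITT result dependent on which section a site followed.

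**Conclusion.** The point holds as an inconsistency in current protocol text with a conditional consequence. Appendix 7 and Section 7.1.2 give different instructions for the same event. Only the literal reading does harm: a dosed child withdrawn before Month 6 becomes an imputed non-responder, even where the test could have been taken.

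On that reading, each of the first three withdrawals costs about 11 to 19 percentage points of power and lowers the expected response rate by about 1.4 to 1.5 points. This rests on an assumed count, a 93% response in the remaining children, and no other missing Month 6 result. On the pause reading the loss is zero. A false-positive risk cannot be inferred, since type I error falls. The sentence should be corrected, but it does not undermine a positive result.

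**What to change.** **1. Protocol Appendix 7.** Replace the withdrawal sentence with:

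> Suspected or confirmed COVID-19 infection may lead to a temporary pause of dosing under Section 7.1.2 and is not in itself a reason for withdrawal from the study; wherever consent holds and the child can attend, the Month 6 GnRH test is taken within the delay allowed in this appendix (no more than 2 weeks).

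**2. SAP 6.1.** Add that a Month 6 GnRH test delayed for COVID-19 under Appendix 7, taken before the second injection, counts as the Month 6 assessment in the primary analysis and is listed as a COVID-19 deviation. State the last acceptable day: Day 183 if the two weeks run from Day 169 (169 + 14), or Day 186 if they run from the end of the window (172 + 14). Without this line a test after Day 172 would fall outside the SAP's Month 6 window and its status would be unclear.

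**Cost.** One protocol sentence by amendment, with the ethics approval that Section 10.1.1 requires, and one SAP line. No new visit or test.

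**Downside.** A delayed test falls past the 169-day release period given in Protocol 4.3 and may show true loss of suppression. Testing still does better than withdrawal, provided the delayed tests count. With three delayed children responding at an assumed 80%, power is 81% (62 treated) or 77% (66); at an assumed 50% it is 68% or 63%. If the three are withdrawn instead, it is 40% or 35%.

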| 6.2 | Unscheduled Visits, Retest, Withdrawal Visit, | 22 |
| 7 | DERIVED DATA (IF APPLICABLE) | 22 |
| 8 | REFERENCES | 23 |
| 9 | APPENDICES | 25 |
| A1. | SAS Code | 25 |
| A2. | Partial/Missing Date Convention | 26 |
| A3. | Programming Convention for Outputs | 28 |
| A4. | Listings Conventions | 28 |
| A5. | Z-score and Percentile for Height for Age | 29 |

LIST OF ABBREVIATIONS AND DEFINITION OF TERMS

| ABBREVIATION | Wording Definition |
|---------------------|--|
| AE | Adverse Event |
| ALT | Alanine Aminotransferase |
| AST | Aspartate Transaminase |
| ATC | Anatomical Therapeutic Chemical |
| BA | Bone Age |
| BLQ | Below the Limit of Quantification |
| BMI | Body Mass Index |
| C | Concomitant |
| CA | Chronological Age |
| CI | Confidence Interval |
| CRF | Case Report Form |
| CPP | Central Precocious Puberty |
| eCRF | Electronic Case Report Form |
| CSR | Clinical Study Report |
| CTCAE | Common Terminology Criteria for Adverse Events |
| DMC | Data Monitoring Committee |
| ECG | Electrocardiogram |
| EDC | Electronic Data Capture |
| EOS | End of Study |
| EMA | European Medicines Agency |
| FDA | Food and Drug Administration |
| FSH | Follicle-stimulating Hormone |
| GnRH | Gonadotropin-releasing Hormone |
| ICE | Intercurrent Event |
| ICH | International Conference on Harmonisation |
| IGF-1 | Insulin-like Growth Factor 1 |
| i.m. | Intramuscular |
| IMP | Investigational Medicinal Product |
| ITT | Intention-To-Treat |
| IU | International Units |
| i.v. | Intravenous |

| ABBREVIATION | Wording Definition |
|---------------------|--|
| LH | Luteinising Hormone |
| LLOQ | Lower Limit of Quantification |
| MedDRA | Medical Dictionary for Regulatory Activities |
| mITT | Modified Intention-To-Treat |
| NCI-CTCAE | National Cancer Institute – Common Terminology Criteria for Adverse Events |
| NRI | Non-responder imputation |
| P | Prior |
| PASS | Power Analysis and Sample Size |
| PC | Prior and Concomitant |
| PK | Pharmacokinetic |
| PN | Preferred Name |
| PP | Per Protocol |
| PR | Prolonged Release |
| PT | Preferred Term |
| SAE | Serious Adverse Event |
| SAP | Statistical Analysis Plan |
| SAS® | Statistical Analysis System® |
| SD | Standard Deviation |
| SDTM | Study Data Tabulation Model |
| SE | Standard Error |
| SI | International System of Units |
| SOC | System Organic Class |
| SP | Service Provider |
| TEAE | Treatment Emergent Adverse Event |
| TFLs | Tables, Figures and Listings |
| ULOQ | Upper Limit of Quantification |

1 INTRODUCTION

The purpose of this Statistical Analysis Plan (SAP) is to outline the planned analyses to be completed to support the completion of the Clinical Study Report (CSR) for protocol D-CN-52014-244. It describes the rules and conventions to be used in the analysis and presentation of data, the data to be summarised and analysed, including specificities of the statistical analyses to be performed.

Exploratory analyses not necessarily identified in this SAP may be performed to support the clinical development program. Any post-hoc, or unplanned, analyses not identified in this SAP performed will be clearly identified in the respective CSR.

The SAP is to be finalised before first participant in. A separate shell will be provided for tables, figures and listings.

Any deviations from the SAP after database lock will be documented in the CSR (section 9.8 “Changes in the conduct of the study or planned analyses” as per International Conference on Harmonisation (ICH) E3).

2 PROTOCOL OVERVIEW

2.1 Study Objectives and Hypotheses

2.1.1 Primary Objective

The primary objective of the study is to assess the efficacy of the triptorelin 6-month prolonged release (PR) formulation in suppressing luteinizing hormone (LH) levels to prepubertal levels (defined as a peak LH ≤ 5 IU/L) after intravenous (i.v.) gonadotropin-releasing hormone (GnRH) stimulation at Month 6 (Day 169) in Chinese children with central precocious puberty (CPP).

2.1.2 Secondary Objectives

The secondary objectives of the study are as follows:

- To assess the efficacy in suppressed LH response to GnRH test at Months 3 and 12
- To assess change of basal serum LH and FSH levels at Months 3, 6, 9 and 12
- To assess change of peak serum LH and FSH levels after the GnRH stimulation test at Months 3, 6 and 12
- To assess sex hormone serum concentrations (oestradiol for girls and testosterone for boys) at Months 3, 6, 9 and 12
- To assess height (Z-score [height for age] and percentile for height for age) growth velocity and BA (Greulich and Pyle method) at Months 6 and 12
- To assess sexual maturation at Months 6 and 12
- To assess uterine length in girls and testis volumes in boys at Months 6 and 12
- To assess the change of body weight and BMI at Months 6 and 12
- To assess the safety profile
- To evaluate local tolerability at the injection site immediately and 2 hours after triptorelin injection
- To assess the PK of plasma triptorelin

2.1.3 Hypotheses

The null hypothesis H0: $P \leq 80\%$ versus the alternative hypothesis H1: $P > 80\%$, where P is the proportion of children with LH suppression defined as stimulated peak LH ≤ 5 IU/L after

GnRH stimulation at Month 6.

2.2 Overall Study Design and Investigational Plan

This is an open-label, multicentre, single arm interventional study to evaluate the efficacy and safety of triptorelin 6-month formulation in Chinese paediatric participants with CPP over a period of 12 months.

This study aims to demonstrate that triptorelin 6-month formulation is efficacious in suppressing luteinizing hormone (LH) to prepuberal levels in children with CPP (defined as a peak LH ≤ 5 IU/L after intravenous (i.v.) gonadotropin-releasing hormone (GnRH) stimulation) at Month 6.

This study will enrol Chinese participants with CPP in girls less than 9 years old and boys less than 10 years old at initiation of triptorelin treatment.

Approximately a total 66 participants (including at least three boys) will be enrolled to be administered intramuscular (i.m.) injections of triptorelin on Day 1 and Month 6 of the study. The triptorelin injection dose will not be adapted based on body weight.

[figure not shown]
The study consists of a Screening period (the Screening visit will take place up to 28 days before enrolment), during which participants with CPP will be screened for eligibility. Participants will receive triptorelin injections on Day 1 and Month 6 of the study. Participants will have study visits at Screening, Day 1 and at Months 3, 6, 9 and 12 (Figure 1).

Each participant is expected to be enrolled in this study for a minimum of 12 months and up to 13 months (including Screening period).

Participants who complete the study will perform final procedures and assessments at the final visit (Month 12). Participants who withdraw from the study before the completion of the evaluation period will be invited to attend an Early Withdrawal visit to perform early discontinuation procedures and assessments.

The study design is illustrated in Figure 1.

Figure 1 Study Design

